#### 208833 (STAPH AUREUS BIOCONJ-001 STG) Protocol Amendment 6 Final

#### JCI

e Visit 2 and 6: Clinical visit for PoP Step 1 subjects (i.e. first 40 subjects enrolled in the PoP) where 6 mL of whole blood for safety laboratory evaluation will be collected; Phone call for PoP Step 2 subjects (i.e. all those following subjects after the first 40 enrolled in the PoP Step 1).

f Remind subjects that the device is now ready to collect after Dose 2 data.

 The blood sampling for safety lab evaluation only (~6 mL to be drawn from PoP Step 1 subject only) should occur on Day 1 and Day 61 but, as an alternative, can be performed up to 1 day before vaccine administration.

hUnscheduled visits can occur at any time after first study vaccination and should happen as soon as possible after signs/symptoms onset

Occurrence of solicited AEs within 30 minutes post vaccination observation must be recorded in the eCRF

a/b = vaccine/placebo

pIMDs = potential Immune-Mediated Diseases SAE = Serious Adverse Event Vac = Vaccination M = Month V = Visit
Whenever possible, the investigator should arrange study visits within the intervals described in Table 5 and Table 6.

| Table 5 | Intervals between study visits (dose-escalation safety lead-in |
|---------|--|
|         | epochs)  |

| Groups     | Interval  | Optimal Length of | Allowed        |
|------------|---|-------------------|----------------|
|            |   | interval          | interval       |
| Group 1a/b | V0-Grp1-3 (Day -1)→ V1-Grp1-3 (Day 1)                     | 1 days            | 0 - 3 days *   |
| Group 2a/b | V1-Grp1-3 (Day 1)→ V2-Grp1-3 (Day 8)                      | 7 days            | 7 - 8 days     |
| Group 3a/b | V1-Grp1-3 (Day 1)→ V3-Grp1-3 (Day 31)                     | 30 days           | 30 - 33 days   |
|            | V1-Grp1-3 (Day 1)→ V4-Grp1-3 (Month 6, Day 181)           | 180 days          | 180 - 190 days |
|            | V1-Grp1-3 (Day 1) $\rightarrow$ V5-Grp1-3 (Month 12, Day  | 365 days          | 365 - 380 days |
|            | 366)  |                   |                |
| Group 4a/b | V0-Grp4 (Day $-1$ ) $\rightarrow$ V1-Grp4 (Day 1)         | 1 days            | 0 - 3 days *   |
|            | V1-Grp4 (Day 1) $\rightarrow$ V2-Grp4 (Day 8)             | 7 days            | 7 - 8 days     |
|            | V1-Grp4 (Day 1)→ V3-Grp4 (Day 31)                         | 30 days           | 30 - 33 days   |

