### Table 6 Intervals between study visits (PoP epochs)

| Group 5a/b   | Interval  | Length of
interval | Allowed interval |
|--------------|---|-----------------------|------------------|
| All subjects | V0 (Day -30 up to Day 1) $\rightarrow$ V1 (Day 1) | up to 30 days         | 0 - 30 days*     |
|              | V1 (Day 1)→V2 (Day 8)                             | 7 days                | 7 - 9 days       |
|              | V1 (Day 1)→V3 (Day 15)                            | 14 days               | 14 - 21 days     |
|              | V1 (Day 1)→V4 (Day 31)                            | 30 days               | 30 - 37 days     |
|              | V1 (Day 1)→V5 (Day 61)                            | 60 days               | 60 - 67 days     |
|              | V5 (Day 61)→V6 (Day 68)                           | 7 days                | 7 - 9 days       |
|              | V5 (Day 61)→V7 (Day 75)                           | 14 days               | 14 - 21 days     |
|              | V5 (Day 61)→V8 (Month 3, day
91)               | 30 days               | 30 - 40 days     |
|              | V5 (Day 61)→V9 (Month 8, day 241)                 | 180 days              | 180 - 190 days   |
|              | V5 (Day 61)→V10 (Month 14, day 426)               | 365 days              | 365 - 380 days   |

a/b = vaccine/placebo; PoP = Proof of Principle; V = Visit

Note: CDISC is not calculating with Day 0, i.e. interval between Day -30 and Day 1 is 30 days.

\* Vaccination should occur after clinical resolution of culture confirmed SSTI caused by S. aureus and must occur within 30 days from the date of skin drainage for microbiology assessment (done either outside or in the study)

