# 4. OBJECTIVE(S) AND ENDPOINT(S)

#### Objectives Endpoints Primarv Descriptive: Occurrence and intensity of solicited local and general AEs • during 7 days after each dose (i.e. day of vaccination and To assess safety and reactogenicity of the 6 subsequent days) in all subjects by vaccination group. investigational S. aureus vaccine Occurrence, intensity and relationship to vaccination of unsolicited AEs during 30 days after each dose (i.e. day of injection and the 29 subsequent days) in all subjects by vaccination group. Occurrence, intensity and relationship to vaccination of all SAEs in all subjects by vaccination group: Groups 1 to 3 from Day 1 (day of vaccination) until Day 366. Groups 4 and 5 from Day 1 (day of vaccination) until Dav 426. Occurrence, intensity and relationship to vaccination of all potential immune-mediated disease (pIMDs) during in all subjects by vaccination group. Groups 1 to 3 from Day 1 (day of vaccination) until Day 366. Groups 4 and 5 from Day 1 (day of vaccination) until Day 426. Occurrence of haematological and biochemical laboratory abnormalities, and changes from the baseline values after vaccination: In all subjects of Groups 1 to 3 on Day 8. In all subjects of Group 4 on Days 8 and 68 (i.e. 7 days after dose 1 and dose 2), respectively. Subjects in Group 5 Step 1 (i.e. first 40 subjects enrolled in the PoP) on Days 8 and 68 (i.e. 7 days after dose 1 and dose 2), respectively.

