#### Staggered enrolment in dose-escalation safety lead-in epochs:

Four groups receiving 4 different vaccine formulations will be included in the doseescalation safety lead-in epochs (for details see Section 5.2 and Figure 5). Subjects in the 4 groups will be enrolled in 4 successive steps (see Figure 7), the next group can only be enrolled after safety assessment of the previous group and safety assessment committees (SRT/iSRC) approval. Additionally, for each step/group, a 2-substep staggered design is chosen (see Figure 7):

- Substep a: 1 vaccinated subject + 1 subject receiving placebo (sentinel subjects). The 2 sentinel subjects in each group should be vaccinated on 2 different days. All the available safety data collected up to the Day 8 after vaccination visit from both subjects (including laboratory assessments at Day 8) will be evaluated. The SRT and iSRC Chair will evaluate safety data and confirm the start of the step below. Conditionally; unblinded data may be evaluated by iSRC and only after positive opinion of iSRC the next step can be started.
- Substep b: 5 vaccinated subjects + 1 subject receiving placebo. All the available safety data collected up to the Day 8 after vaccination visit for the last vaccinated subject (including laboratory assessments at Day 8) will be evaluated. The SRT and iSRC Chair will evaluate all the safety data available and confirm the start of the next step (subsequent group). Conditionally; unblinded data may be evaluated by iSRC and only after positive opinion of iSRC the next step can be started. All the unblinded data collected up to Day 8 after vaccination Visit 1 of the fourth group will be reviewed by iSRC.

After the iSRC unblinded data review of dose 1 of the fourth group of the dose-escalation safety lead-in and prior to administering the second vaccine/placebo dose in that fourth group, the staggered enrolment of the first approximately 40 subjects in the PoP epochs in the vaccine target population (subjects with a recent *S. aureus* SSTIs) can start.

The fourth group will receive a second vaccine/placebo dose with an interval of approximately 2 months and subjects of all the groups will be followed until study end (i.e. for each subject approximately 12 months after last vaccination).

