#### 8.6.2. Outcome of safety evaluation

- If no safety signal is observed, the favourable outcome of the safety evaluations will be documented and provided in writing (scanned and e-mailed), authorising the investigator to start vaccination of subjects with the subsequent dose as well as enrolment and vaccination of the remaining subjects in the next step of the study, as applicable.
- In case the investigator becomes aware of holding rule(s) 1 is met, he/she should immediately inform GSK of the event (Refer to Table 24 for contact information).
- If a safety signal is observed during the safety evaluations or if any of the holding rules 2a-c is met, the iSRC Chair (or his/her representative) is responsible for the urgent communication to GSK, including the rationale for the decision to put the vaccination on hold or not.
- All site staff will be informed about that final decision (suspend or continue the study) by their local GSK contact. CRDL who is the primary contact will inform the local GSK contact.

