| 2a              | Any Grade 3 solicited local AE (lasting 48h
or more) in an investigational group, within
the 7-day (Day 1-7) post-vaccination period  | ≥1   | ≥ 6/30 or 20%   | N/A   |
| 2b              | Any Grade 3 solicited general AE (lasting
48h or more) in an investigational group,
within the 7-day (Day 1-7) post-vaccination
period   | ≥1   | ≥ 6/30 or 20%   | N/A   |
| 2c              | Any Grade 3 unsolicited AE in an
investigational group, that cannot
reasonably be attributed to a cause other
than vaccination, within the 7-day (Day 1-7)
post-vaccination period or any Grade 3
abnormality in pre-specified haematological
or biochemical laboratory parameters in an
investigational group within the 7-day (Day
1-7) post-vaccination period * | ≥1   | ≥ 6/30 or 20%   | N/A   |

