#### 8.6.5. Safety review team (SRT)

The SRT is a GSK's Central Committee responsible for on-going safety monitoring of the entire project and will meet on a regular basis throughout the duration of the study. In order to keep blinded all people involved in the conduct, cleaning and final analysis of the study, the SRT will monitor safety in a blinded manner. The GSK Biologicals' SRT and iSRC chair will jointly review blinded safety data. If no potential holding rules (e.g. 1a, 1b or 1c, Table 26) or safety concerns are identified during this blinded review, then review of unblinded data by iSRC team may not be required and study can proceed with the next step. Should there be any concerns that would require the evaluation of unblinded safety data, the iSRC will perform unblinded review of safety data and proceed as specified in the iSRC charter.

Refer to the iSRC Charter for details about the safety assessment committees evaluation.

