# 12.5.8.1. Time period for detecting and recording adverse events, serious adverse events and pregnancies

All solicited AEs during 7 days following administration of each dose of study vaccine(s) (Day 1 to Day 7 and Day 61 to Day 67) must be recorded in the eDiary, irrespective of intensity or whether or not they are considered vaccination-related.

All other AEs during 30 days following administration of each dose of study vaccine(s) (Day 1 to Day 30 and Day 61 to Day 90) must be recorded in the appropriate section of the eCRF, irrespective of intensity or whether or not they are considered vaccination-related.

The time period for collecting and recording SAEs will begin at the first receipt of study vaccine(s) and will end 366 days following administration of the last dose of study vaccine(s) for each subject (i.e. the last study visit for each subject). See Section 12.5.9 for instructions on reporting of SAEs. However, any SAEs assessed as related to study participation (e.g. study treatment, protocol-mandated procedures, invasive tests, or change in existing therapy) or related to a GSK product will be recorded from the time a subject consent to participate in the study.

All AEs/SAEs leading to withdrawal from the study will be collected and recorded from the time of the first receipt of study vaccine(s).

In addition to the above-mentioned reporting requirements and in order to fulfil international reporting obligations, SAEs that are related to study participation (i.e. protocol-mandated procedures, invasive tests, a change from existing therapy) or are related to a concurrent GSK medication/vaccine will be collected and recorded from the time the subject consents to participate in the study until she/he is discharged from the study.

The time period for collecting and recording pregnancies will begin at the first receipt of study vaccine(s) and will end 366 days following administration of the last dose of study vaccine(s) (i.e. the last study visit for each subject). See Section 12.5.9 for instructions on reporting of pregnancies.

The time period for collecting and recording of pIMDs will begin at the first receipt of study vaccine(s) and will end 366 days following administration of the last dose of study vaccine(s) (i.e. the last study visit for each subject). See Section 12.5.9.5 for instructions on reporting of pIMDs.

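### The laboratory part of holding rule 2c covers post-dose Days 1–7, but every scheduled post-dose safety blood is drawn on post-dose Day 8 or later

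*Protocol*

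**What the plan says.** Table 26 in Protocol 8.6.3 has two clauses in rule 2c. One concerns Grade 3 unsolicited AEs. The other concerns Grade 3 values in pre-specified haematological "or biochemical laboratory parameters in an investigational group within the 7-day (Day 1-7) post-vaccination period". The threshold is one subject in the dose-escalation lead-in and 6 of 30 (20%) in PoP Step 1. The rule does not apply in PoP Step 2.

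The 7-day period is fixed elsewhere. Section 4 describes it as the vaccination day and the six days after it, and Section 12.5.8.1 gives the calendar days for solicited events: "Day 1 to Day 7 and Day 61 to Day 67) must be recorded in the eDiary".

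Post-dose haematology and chemistry are scheduled only at the Day 8 and Day 68 visits (Section 8.5.7, Table 25). Section 4 describes the timing for Group 4 as "In all subjects of Group 4 on Days 8 and 68 (i.e. 7 days after dose 1 and dose 2), respectively". The allowed intervals are in Section 2. In Table 5, "V1-Grp1-3 (Day 1)→ V2-Grp1-3 (Day 8") may be 7 to 8 days. In Table 6, "V5 (Day 61)→V6 (Day 68") may be 7 to 9 days.

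The results are used. Section 8.6.1 requires that at each lead-in substep the available safety data ("including laboratory assessments at Day 8) will be evaluated".

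**The concern.** The clause and the sampling schedule miss each other. If Day 1 is the day of the dose, a sample taken 7 days later falls on Day 8, one day after the rule's window has closed. No visit window allows an earlier draw. A Grade 3 result on an on-schedule sample would therefore not formally meet the rule that appears to have been written for it.

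This is a first-in-human escalation, and in the lead-in one such value in an investigational group is meant to be enough. Rule 2 is assessed on unblinded data. However, Section 8.6.6 predefines unblinded iSRC review only after dose 1 in Group 4 and after dose 1 in PoP Step 1. For Groups 1–3 the step review is blinded, and under Section 8.6.5, if it identifies no potential holding rule or safety concern, "then review of unblinded data by iSRC team may not be required and study can proceed with the next step". If a Grade 3 Day 8 value is not a potential rule 2c event, its escalation depends on the blinded reviewers choosing to treat it as a concern. The same conditional review applies to the Group 4 sentinel substep and to the Group 4 Day 68 data that gate dose 2 in PoP Step 1.

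**Working it through.** **The plan's own figures.** Section 8.6.4 gives the operating characteristics of rules 2a–c. They are binomial tail probabilities and reproduce as follows.

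| Setting | Trigger | True rate | Quantity | Calculated | Stated |
|---|---|---|---|---|---|
| Lead-in, n = 6 | ≥1 | 25% | met: 1 − 0.75^6 | 82.2% | more than 82% |
| Lead-in, n = 6 | ≥1 | 10% | not met: 0.90^6 | 53.1% | more than 53% |
| PoP Step 1, n = 30 | ≥6 | 25% | met: P(X ≥ 6) | 79.7% | more than 80% |
| PoP Step 1, n = 30 | ≥6 | 10% | not met: P(X ≤ 5) | 92.7% | more than 93% |

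The small shortfalls at n = 30 are rounding. These figures assume that every qualifying event is counted by the rule.

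**Timing.** With the vaccination day as Day 1 (Protocol 12.5.8.1; SAP 10.1.3.6 uses the same convention for onset day), post-dose day = interval in days + 1. The rule's window is post-dose Days 1–7.

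| Draw | Source | Allowed interval | Post-dose day | Days within 1–7 |
|---|---|---|---|---|
| Groups 1–3, V1 to V2 | Table 5 | 7–8 | 8–9 | none |
| Group 4 dose 1, V1 to V2 | Table 5 | 7–8 | 8–9 | none |
| Group 4 dose 2, V4 to V5 | Table 5 | 7–9 | 8–10 | none |
| PoP Step 1 dose 1, V1 to V2 | Table 6 | 7–9 | 8–10 | none |
| PoP Step 1 dose 2, V5 to V6 | Table 6 | 7–9 | 8–10 | none |

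The earliest allowed draw is one day after the window closes and the latest is three days after. The other scheduled draws do not help. Day −1 (Groups 1–4) and Day 1 (PoP Step 1) precede dose 1. Day 61 (Group 4 and PoP Step 1) precedes dose 2 and is 60 days after dose 1.

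**Number of draws affected.**

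- All subjects: Groups 1–3, 24 × 1 = 24; Group 4, 8 × 2 = 16; PoP Step 1, about 40 × 2 = 80. Total about 120.
- Vaccine recipients: 18 × 1 + 6 × 2 + 30 × 2 = 18 + 12 + 60 = about 90.

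**Effect on the clause.** With on-schedule samples only, the chance of meeting the laboratory clause is 0% at any true rate. If the window reached the visit sample and its allowance (up to post-dose Day 10), all five rows would fall inside it and the probabilities in the first table would apply.

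**Can Day 8 be read into the window?** Section 8.6.3 itself puts Day 8 on the other side of the line: it says no formal holding rule applies to unsolicited AEs collected from Day 8 to Day 30. Section 8.5.7 has clinically relevant laboratory changes recorded as AEs, so a Day 8 finding entered that way falls outside the AE clause too. Reading the window loosely as seven days after the dose would admit Day 8 but still not the allowed draws on Days 9 and 10.

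**The case against.** The strongest reply is that little is lost in practice. Day 8 laboratory data must be evaluated before each lead-in step proceeds, and unblinded review is predefined after dose 1 in Group 4 and in PoP Step 1. Section 8.6.2 sends a signal and a met rule down one route: "If a safety signal is observed during the safety evaluations or if any of the holding rules 2a-c is met", the iSRC Chair communicates urgently with the sponsor and gives reasons for holding or not holding. A met rule 2c is thus a formal label rather than an automatic stop. The intent also seems clear. The sample is described as taken 7 days after the dose, and the Amendment 2 rationale links safety bloods to the laboratory holding rules, so a committee would probably apply the rule to it. The iSRC charter, which is not among the documents, may already settle the matter.

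Much of this stands. An unscheduled draw before Day 8 could also count, the AE clause works within its own window, and Grade 4 laboratory values are SAEs under Section 12.5.2 and, if life-threatening, could meet rule 1a. The practical effect is therefore limited. None of it makes the Grade 3 laboratory trigger work as written.

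A further argument is that the conditional unblinding in Groups 1–3 comes from the review structure, so correcting the window would change nothing there. This is only partly right. Section 8.6.5 names rules 1a, 1b and 1c as examples, not as a complete list, so a corrected 2c would make a Grade 3 Day 8 value a potential holding rule for the blinded reviewers. They would still have to recognise it as one.

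**Conclusion.** The concern holds. Taken literally, the laboratory clause of rule 2c cannot be met by any on-schedule sample: no allowed draw day in any of the five schedules falls within Days 1–7. The defect is confined to the formal Grade 3 laboratory trigger in the lead-in and PoP Step 1. It matters most for the 18 vaccine recipients in Groups 1–3, and it also touches the two conditional reviews in Group 4.

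This rests on the protocol's own definition of the 7-day period and on samples taken within the allowed intervals. The documents give no expected frequency of Grade 3 laboratory values, so the number of results that would be missed cannot be estimated. It looks like a window-wording error rather than a deliberate choice. It should be corrected because it disables a stated stopping rule in a first-in-human study.

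**What to change.** In Table 26, rule 2c, keep Days 1–7 for the unsolicited-AE clause and give the laboratory clause its own window: any Grade 3 abnormality in the pre-specified haematological or biochemical parameters up to and including the scheduled Day 8 (post-dose 1) or Day 68 (post-dose 2) sample, within that visit's allowed interval. Align the iSRC charter. If the lead-in and PoP Step 1 are already complete, write a short note to file stating how any Grade 3 results at Day 8 or Day 68 were handled against rule 2c.

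The cost is one table entry and a charter alignment, or the note alone. No samples, visits or procedures are added.

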#### Table 26Study holding rules

AE = Adverse Event; SAE = Serious Adverse Event; FTIH = First Time in Human; PoP = Proof of Principle; N/A = Not Applicable

\* Grading of laboratory parameters will be based on the FDA Guidance for Industry "Toxicity Grading Scale for Healthy Adult and Adolescent Volunteers Enrolled in Preventive Vaccine Clinical Trials" (refer to Appendix 7, Section 12.7). Those laboratory parameters not included in the FDA Toxicity Grading Scale will not be graded.

Holding rules 1a (in all steps), 1b and 1c (during the dose-escalation safety lead-In epoch and the PoP Step 1) will be monitored by the investigators on a continuous basis for as long as vaccination is ongoing in the study. Meeting any of these holding rules will trigger a hold of vaccination irrespective of the number of subjects vaccinated. Holding rules 2a, 2b and 2c are reviewed during unblinded review in the planned or *ad-hoc* iSRC. These rules will be applied only during the dose-escalation safety lead-In epoch and the staggered enrolment step of PoP vaccination

epoch. Also in this case, different cut-offs are considered based on the sample size of the study group.

For both, the dose-escalation safety lead-in and PoP, the investigator will not be permitted to start the administration of Dose 1 for the next group until receipt of the favourable outcome of the safety assessment committees evaluation (SRT/iSRC), documented and provided in writing (scanned and emailed), authorising the investigator to proceed. The same applies for the administration of Dose 2 in the fourth group of the dose-escalation safety lead-in and for the administration of Dose 2 in the staggered enrolment of first 40 subjects of the PoP epoch.

During the whole study period, if the investigator becomes aware of a holding rule being met, he/she will suspend vaccination and will inform GSK immediately.

The below flow of communication has to be followed:

- The concerned site staff must suspend the vaccination.
- The concerned site staff must immediately inform their local contact defined in the Table 24.
- Local Medical Lead (LML) will inform the other sites of his/her country, LMLs of other countries and the Clinical Research & Development Lead (CRDL).
- All informed site staff will send back an e-mail to their local contact to acknowledge receipt of the information.
- GSK Central will further evaluate the case with the iSRC and will take the decision to stop or to restart the vaccination. CRDL who is the primary contact will inform the local GSK contact. All site staff will be informed about that final decision by their local GSK contact.

The detailed flow of communication will be described in the iSRC Charter.

